12 STATISTICAL CONSIDERATIONS AND DATA ANALYSES

12.1 Sample Size Determination

Sufficient subjects will be screened and entered into the acclimatization period to randomize approximately 234 subjects to investigational product (approximately 117 subjects per treatment group) to ensure approximately 210 complete the study (approximately 105 subjects per treatment group), allowing for approximately 10% dropouts.

The study will be sufficiently powered to demonstrate statistical superiority of the Test Toothpaste compared to the Reference Toothpaste (negative control) for the change from Baseline in the Schiff sensitivity score after 56 days, i.e., 8 weeks, (primary objective) and 3 days (key secondary objective, earliest time point) treatment. It is anticipated that the treatment effect will increase over time. A sample size of 105 evaluable subjects per treatment group will provide 90% power to detect a mean difference of 0.25 units ($SD = 0.55$) in change from Baseline in Schiff sensitivity score after 3 days treatment, using a 2-tailed 2-sample t-test with a 5% significance level. The sample size calculation was performed using PASS software version 23.0.1.

The dropout rate and SD estimates are based on the results of DH efficacy studies of similar design and duration (Clinical Studies **CCI** [REDACTED] and **CCI** [REDACTED] sponsor data held on file, available on request).

Property of Haleon- Confidential

May not be used, divulged, published or otherwise disclosed without the consent of Haleon

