3 STUDY OBJECTIVES AND ENDPOINTS

| Objectives | Endpoints |
|---|--|
| Efficacy | |
| Primary | |
| To demonstrate the clinical efficacy of a 5% CSPS toothpaste in reducing DH to an evaporative (air) stimulus (as measured by Schiff sensitivity score), compared to a negative control toothpaste, after 8 weeks twice daily use. | Change from Baseline in Schiff sensitivity score at Day 56 (Week 8). |
| Secondary | |

| | |
|---|---|
| To demonstrate the clinical efficacy of a 5% CSPS toothpaste in reducing DH to a tactile stimulus (as measured by tactile threshold in grams [g]), compared to a negative control toothpaste, after 8 weeks twice daily use. | Change from Baseline in tactile threshold (g) at Day 56 (Week 8). |
| To investigate the clinical efficacy of a 5% w/w CSPS toothpaste in reducing DH to evaporative (air) and tactile stimuli (as measured by Schiff sensitivity score and tactile threshold (g), respectively), compared to a negative control toothpaste, after 3-, 7-, 14- and 28-days twice daily use. | Change from Baseline in Schiff sensitivity score at Days 3, 7, 14 & 28. Change from Baseline in tactile threshold (g) at Days 3, 7, 14 & 28. |
| To describe subject-perceived changes in oral health-related quality of life (OHRQoL), as measured by the Dentin Hypersensitivity Experience Questionnaire (DHEQ-48), after 4- and 8-weeks twice daily use of their assigned investigational toothpaste. | 
At Day 28 (Week 4) & Day 56 (Week 8): Change from Baseline in DHEQ-48 endpoints.
 
Section 1
 
 Impact on Everyday Life (Q7-9) 
Section 2
 
 Total Score (Q1-34) Individual Domain Scores 
 Restrictions (Q1-4) Adaptation (Q5-16) Social Impact (Q17-21) Emotional Impact (Q22-29) Identity (Q30-34) Global Oral Health Score (Q35) Effect on Life Overall Score (Q36-39) |
| Exploratory | |
| To investigate subject satisfaction with their assigned investigational toothpaste for the overall management of DH, as measured by a Numeric Rating Scale (NRS), after 8 weeks treatment. | At Day 56 (Week 8): Satisfaction NRS score |
| Safety | |
| To monitor the safety and oral tolerability of the investigational toothpastes over 8 weeks twice daily use. | Treatment emergent adverse events (TEAEs). |

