- Earlier assessment time points (3-, 7-, 14- and 28-days) will also be included in the study design to investigate time to onset of DH relief.

On completion of the Baseline assessments, the clinical examiner will select two ‘Test Teeth’ from those that qualify at both Screening (Visit 1) and Baseline (Visit 2) for assessment of tactile and evaporative (air) sensitivity at all subsequent visits. Qualifying subjects will be stratified according to the maximum Schiff sensitivity score of their two selected ‘Test Teeth’ to ensure treatment groups are balanced for DH severity. Repeated stimulation of multiple sensitive teeth may alter the pain response as testing continues around the mouth; the anticipation of pain or discomfort with protracted testing, along with the discomfort of having to keep the mouth open for an extended period of time, may also affect subject perception of pain ([Holland, 1997](#)). Thus, the selection of two representative ‘Test Teeth’ to evaluate changes in DH with treatment is common practice in DH efficacy studies. To be representative of different areas of the mouth, with independent innervation, ‘Test Teeth’ should be non-adjacent and in different quadrants.

To help minimize exposure to environmental triggers for sensitivity prior to clinical DH assessment, subjects will be instructed to refrain from oral hygiene, chewing gum, eating and drinking for a period of time prior to their arrival at the investigator site.

Property of Haleon- Confidential

May not be used, divulged, published or otherwise disclosed without the consent of Haleon

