12.3 Statistical Analyses

This is a summary of the planned statistical analyses; the detail of the proposed statistical analyses will be documented in the Statistical Analysis Plan (SAP), to be written following finalization of the protocol and prior to study unblinding.

The mITT population will be used for all efficacy analyses.

All p-values presented will be two-sided and assessed at the 5% significance level. A sequential testing strategy will be used to adjust for multiplicity for the comparisons between the Test and Reference Toothpastes in change from Baseline in Schiff sensitivity score and tactile threshold (g) at each assessment time point.

At each timepoint, change from Baseline in tactile threshold (g) will only be assessed for confirmatory evidence if the change from Baseline in Schiff sensitivity score achieves a statistically significant greater reduction for the Test Toothpaste compared to Reference Toothpaste (negative control). This strategy will begin at Day 56, then move to successively earlier timepoints (i.e., Day 56 → Day 28 → Day 14 → Day 7 → Day 3), only moving the next earlier timepoint for confirmatory evidence if all later timepoints achieve statistically significant greater reductions for the Test Toothpaste compared to Reference Toothpaste (negative control) for both Schiff sensitivity score and tactile threshold (g). There will be no further adjustments for multiplicity for the other secondary endpoints (DHEQ-48).

Summary statistics (mean, median, SE, SD, minimum, maximum) will be presented for each Schiff sensitivity score and tactile threshold (g) outcome variable at each assessment time point. Raw means (\pm SE) of Schiff sensitivity score and tactile threshold (g) at each assessment timepoint will be plotted by treatment group.

The results from each MMRM will be tabulated, presenting the following information, in addition to the results specified for the primary and secondary analyses below: least square mean change from Baseline for each investigational product at Days 3, 7, 14, 28 and 56 (based on the observed stratification margins for those MMRM with a term for randomized strata) and used to test for any change from Baseline, with two-sided p-values and 95% CIs.

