12.3.1 Primary Endpoint Analysis

The primary endpoint of this study is the change from Baseline in Schiff sensitivity score at Day 56 (Week 8); the primary hypothesis test will be the comparison between the Test Toothpaste and the Reference Toothpaste (negative control) in the mITT population.

Schiff sensitivity score will be derived as the mean score for the two 'Test Teeth' (selected at Baseline). Change from Baseline will be derived for each individual tooth first before calculating mean change for the two 'Test Teeth' where change from Baseline in Schiff sensitivity score at Day X is defined as [(Schiff sensitivity score at Day X) minus (Baseline Schiff sensitivity score)].

Change from Baseline in Schiff sensitivity score at Day 56 will be analysed using a MMRM with investigational product, visit and [investigational product x visit] interaction as fixed effects, and Baseline Schiff sensitivity score as a covariate. Subject will be included as a repeated measure with unstructured covariance matrix. Kenward-Rogers degrees of freedom approach will be applied ([Kenward, 1997](#)). The difference between the least square mean changes from Baseline for the Test Toothpaste compared to Reference Toothpaste (negative control) at Day 56 from the MMRM will be presented, along with the two-sided p-value and 95% CIs.

The assumptions of normality and homogeneity of variance in the MMRM will be investigated. In case of violation of these assumptions, a suitable non-parametric test (adjusted for the randomization stratification) will be performed to assess the change from Baseline comparison (Test Toothpaste vs. Reference Toothpaste at Day 56); the results will be provided to support the MMRM results.

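### Does the 90% power quoted for Day 3 Schiff score overstate the chance of a confirmed Day 3 claim?

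*Protocol*

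**What the plan says.** Protocol 12.1 and SAP 1.4 carry the same paragraph. It opens with a general claim, "The study will be sufficiently powered to demonstrate statistical superiority of the Test Toothpaste" over the Reference on change in Schiff score, and applies it to Day 56 (the primary objective) "and 3 days (key secondary objective, earliest time point) treatment". The one calculation offered is "A sample size of 105 evaluable subjects per treatment group will provide 90% power to detect a mean difference of 0.25 units", with SD 0.55, at Day 3, by a two-sided two-sample t-test at 5%. The link to later visits is one sentence: "It is anticipated that the treatment effect will increase over time".

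Protocol 12.3 and SAP 4.4 set a fixed order. At each visit Schiff is tested before tactile threshold. Testing runs backwards from Day 56 through Days 28, 14 and 7 to Day 3, "only moving the next earlier timepoint for confirmatory evidence if all later timepoints achieve statistically significant greater reductions" on both measures. Day 3 Schiff therefore follows four Schiff tests and four tactile tests.

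The planned Schiff analysis is a mixed model for repeated measures with treatment, visit, their interaction, "and Baseline Schiff sensitivity score as a covariate" (Protocol 12.3.1). It is not the unadjusted t-test used for planning.

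For Days 3 to 28 the objectives table says "To investigate the clinical efficacy of a 5% w/w CSPS toothpaste in reducing DH to evaporative (air) and tactile stimuli", and Protocol 4.2 says the early visits "will also be included in the study design to investigate time to onset of DH relief".

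**The concern.** The paragraph says the trial is powered to show superiority at Day 3 and supports this with the power of one test taken alone. A Day 3 result is confirmatory only if that test and the eight before it all succeed. That joint probability cannot exceed the power of the Day 3 test as actually run, and it falls short unless the earlier tests almost always succeed when Day 3 does.

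The inputs needed to work it out are absent. There is no tactile difference or SD, no numerical Schiff effect after Day 3, and no correlation between visits or measures. Redaction does not explain this: the blacked-out text in that section hides study identifiers, and those studies are cited only for the dropout rate and SD.

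The Day 3 calculation is also the only one behind 105 per arm, and the verb used in 12.1 is stronger than the *investigate* of the objectives table. A reader could take the trial to have a 90% chance of confirming onset at Day 3 when the true chance might be well below that.

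**Working it through.** **1. Reproduce the stated figure.** Inputs from Protocol 12.1: difference 0.25, SD 0.55, 105 per arm, two-sided 5%.

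- Standard error = 0.55 × √(2/105) = 0.0759.
- Noncentrality = 0.25 / 0.0759 = 3.29, on 208 degrees of freedom.
- Noncentral-t power = 0.906 (normal approximation 0.909). The smallest n reaching 90% is 103 per arm.
- Dropout: 105/0.9 = 116.7, so 117 per arm; 210/0.9 = 233.3, so 234.

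The plan's figures are right for the test they name.

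**2. The primary endpoint.** Day 56 Schiff is tested first. If its difference is at least 0.25 with SD 0.55, its power is at least 0.906, whatever happens later in the sequence.

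**3. What the earlier Schiff tests cost.** The plan expects growth but gives no sizes. As an assumption, take differences of 0.25, 0.30, 0.35, 0.40 and 0.45 at Days 3, 7, 14, 28 and 56, with SD 0.55. Powers at 105 per arm are 0.9063, 0.9758, 0.9957, 0.9995 and 1.0000. The chances of missing add up to 0.0937 + 0.0242 + 0.0043 + 0.0005 + 0.0000 = 0.1227. So all five succeed with probability at least 1 − 0.1227 = 0.877, whatever the correlations. Simulation with between-visit correlation 0.6 to 0.8 gives 0.897 to 0.904. With slower growth the figures are 0.864 to 0.885 (to 0.35) and 0.816 to 0.852 (to 0.30).

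**4. What the tactile tests cost.** Nothing in either document sizes them, so these are illustrations only: 400,000 draws of ten normal test statistics, visit correlation 0.6 to 0.8, correlation between measures 0.3 to 0.5, Schiff growing to 0.45, and success required on the first nine tests. The numbers are 105 per arm unless stated.

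| Tactile assumption | Joint power to Day 3 Schiff |
|---|---|
| 80% at every visit | 0.50–0.59 |
| 90% at every visit | 0.67–0.73 |
| 95% at every visit | 0.77–0.81 |
| 99% at every visit | 0.87–0.88 |
| 80% at Day 7, then growing with Schiff | 0.68–0.72 |
| Same effect as Schiff in SD units | 0.88–0.89 |
| Same, 117 per arm | 0.92 |
| 99% at every visit, Baseline adjustment (assumed correlation 0.4) | 0.91–0.92 |

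The bottom two rows matter because 105 is the number expected to complete Day 56. More subjects may be assessed at Day 3 (power of that test alone at 117 per arm is 0.934), and the planned model adjusts for Baseline.

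**5. How far the choices drive the answer.** With wider correlations (0 to 0.9 between visits, 0 to 0.5 between measures) and the later Schiff tests taken as near certain, constant 80% tactile power gives 0.37 to 0.67. Holding both measures flat at 0.25/0.55 SD gives 0.57 to 0.67, but that contradicts the plan's stated expectation of growth.

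**The case for a change.** The strongest case for a change is that the sentence before the calculation claims more than the calculation shows. The expected growth largely covers the Schiff tests, but it is not quantified and gives no size for the four tactile tests. If tactile power were only 50% per visit, the joint figure would be 0.06 to 0.36 under the wider correlations of step 5. Reporting Day 3 estimates regardless does not answer this, because Protocol 12.3 itself separates confirmatory evidence from the rest. Correct labelling would take one clause.

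Some of that stands. Power for the sequence cannot be checked from the documents, and the power paragraph does not point to the sequence. A short pointer to Protocol 12.3 and SAP 4.4 would do no harm.

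It does not amount to an error. The calculation sentence names its endpoint, visit, difference, SD, sample size and test, so it cannot fairly be read as the power of a ten-test sequence. The plan neither sets nor promises a joint-power target. The contrast of verbs is thin too: Protocol 12.3 places Day 3 in the confirmatory sequence and 12.3.2 lists it as a key secondary endpoint, so 12.1 agrees with the analysis section. Cutting the power claim back to Day 56 could also do damage. The sentence on growth is the only bridge from the Day 3 calculation to Day 56, and losing it would leave the primary power claim with less support.

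**Conclusion.** No change follows; this is missing detail with nothing to gain in the analysis. The 90% is correct as the power of a stand-alone Day 3 Schiff t-test at 105 per arm (0.906). Power for the full sequence to Day 3 cannot be derived: with Schiff growing to 0.45 the illustrations in step 4 run from about 0.50 to 0.92, and every tactile figure, later effect and correlation in them is assumed. They do not show that sequence power is below 90%, nor that it reaches it.

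Whatever the true value, following the plan as written gives the same sample size, test order, type I error control, estimates and confidence intervals. Success rests on Day 56 Schiff alone, which is tested first. The fixed sequence also handles a shortfall at an earlier step as intended: Day 3 simply is not claimed as confirmatory.

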12.2 Populations for Analysis

12.2.1 Definitions of Analysis Populations

The Safety population will comprise all randomized subjects who receive at least one dose of investigational product. Summaries and analyses of this population will be based on the investigational product the subject received.

The primary population for the assessment of efficacy will be a modified intention-to-treat (mITT) population. The mITT population will comprise all randomized subjects who receive at least one dose of investigational product and complete at least one-post Baseline DH efficacy assessment. This population will be based on the investigational product the subject was randomized to. All subjects who receive a randomization number will be considered randomized.

The Per-Protocol (PP) population will comprise all subjects in the mITT population who have at least one DH efficacy assessment considered to be unaffected by protocol deviations.

12.2.2 Exclusions of Data from Analysis

Exclusion of data from any of the planned analyses will be agreed during Blinded Data Review (BDR), prior to database lock. The reason(s) for exclusion of a subject from an analysis population or specific data from an analysis will be documented and, if applicable, listed in the Clinical Study Report (CSR).

A PP analysis will be performed for the primary endpoint if $\geq 10\%$ subjects in the mITT population are excluded from the PP population. Efficacy data determined to have been potentially impacted by a protocol deviation will be excluded from the PP analysis. The decisions as to whether or not a protocol deviation impacts efficacy data and whether to perform a PP analysis will be made during BDR, prior to database lock.

12.3 Statistical Analyses

This is a summary of the planned statistical analyses; the detail of the proposed statistical analyses will be documented in the Statistical Analysis Plan (SAP), to be written following finalization of the protocol and prior to study unblinding.

The mITT population will be used for all efficacy analyses.

All p-values presented will be two-sided and assessed at the 5% significance level. A sequential testing strategy will be used to adjust for multiplicity for the comparisons between the Test and Reference Toothpastes in change from Baseline in Schiff sensitivity score and tactile threshold (g) at each assessment time point.

At each timepoint, change from Baseline in tactile threshold (g) will only be assessed for confirmatory evidence if the change from Baseline in Schiff sensitivity score achieves a statistically significant greater reduction for the Test Toothpaste compared to Reference Toothpaste (negative control). This strategy will begin at Day 56, then move to successively earlier timepoints (i.e., Day 56 → Day 28 → Day 14 → Day 7 → Day 3), only moving the next earlier timepoint for confirmatory evidence if all later timepoints achieve statistically significant greater reductions for the Test Toothpaste compared to Reference Toothpaste (negative control) for both Schiff sensitivity score and tactile threshold (g). There will be no further adjustments for multiplicity for the other secondary endpoints (DHEQ-48).

Summary statistics (mean, median, SE, SD, minimum, maximum) will be presented for each Schiff sensitivity score and tactile threshold (g) outcome variable at each assessment time point. Raw means (\pm SE) of Schiff sensitivity score and tactile threshold (g) at each assessment timepoint will be plotted by treatment group.

The results from each MMRM will be tabulated, presenting the following information, in addition to the results specified for the primary and secondary analyses below: least square mean change from Baseline for each investigational product at Days 3, 7, 14, 28 and 56 (based on the observed stratification margins for those MMRM with a term for randomized strata) and used to test for any change from Baseline, with two-sided p-values and 95% CIs.

12.3.1 Primary Endpoint Analysis

The primary endpoint of this study is the change from Baseline in Schiff sensitivity score at Day 56 (Week 8); the primary hypothesis test will be the comparison between the Test Toothpaste and the Reference Toothpaste (negative control) in the mITT population.

Schiff sensitivity score will be derived as the mean score for the two 'Test Teeth' (selected at Baseline). Change from Baseline will be derived for each individual tooth first before calculating mean change for the two 'Test Teeth' where change from Baseline in Schiff sensitivity score at Day X is defined as [(Schiff sensitivity score at Day X) minus (Baseline Schiff sensitivity score)].

Change from Baseline in Schiff sensitivity score at Day 56 will be analysed using a MMRM with investigational product, visit and [investigational product x visit] interaction as fixed effects, and Baseline Schiff sensitivity score as a covariate. Subject will be included as a repeated measure with unstructured covariance matrix. Kenward-Rogers degrees of freedom approach will be applied ([Kenward, 1997](#)). The difference between the least square mean changes from Baseline for the Test Toothpaste compared to Reference Toothpaste (negative control) at Day 56 from the MMRM will be presented, along with the two-sided p-value and 95% CIs.

The assumptions of normality and homogeneity of variance in the MMRM will be investigated. In case of violation of these assumptions, a suitable non-parametric test (adjusted for the randomization stratification) will be performed to assess the change from Baseline comparison (Test Toothpaste vs. Reference Toothpaste at Day 56); the results will be provided to support the MMRM results.

12.3.2 Secondary Endpoint Analyses

Tactile Threshold at Day 56

Tactile threshold (g) will be derived as the mean value for the two 'Test Teeth' (selected at Baseline). Change from Baseline will be derived for each individual tooth first before calculating mean change for the two 'Test Teeth' where change from Baseline in tactile threshold (g) at Day X is defined as [(tactile threshold at Day X) minus (Baseline tactile threshold)].

Key secondary endpoint, change from Baseline in tactile threshold (g) at Day 56, will be analysed using the same MMRM as the primary endpoint but with Baseline tactile threshold (g) as a covariate (rather than Baseline Schiff sensitivity score). In addition, the maximum Baseline Schiff sensitivity score of the two 'Test Teeth' (2 or 3) will be fitted as a fixed effect. The difference between the least square mean changes from Baseline for the Test Toothpaste compared to Reference Toothpaste (negative control) at Day 56 from the MMRM will be

Property of Haleon- Confidential

May not be used, divulged, published or otherwise disclosed without the consent of Haleon

presented, along with the two-sided p-value and 95% CIs.

Tactile Threshold/Schiff Sensitivity Score at Day 28, Day 14, Day 7 and Day 3

The other key secondary endpoints:

- Change from Baseline in Schiff sensitivity score at Day 28
- Change from Baseline in tactile threshold (g) at Day 28
- Change from Baseline in Schiff sensitivity score at Day 14
- Change from Baseline in tactile threshold (g) at Day 14
- Change from Baseline in Schiff sensitivity score at Day 7
- Change from Baseline in tactile threshold (g) at Day 7
- Change from Baseline in Schiff sensitivity score at Day 3
- Change from Baseline in tactile threshold (g) at Day 3

will be analyzed using the same MMRM models described above for Schiff sensitivity score and tactile threshold (g), respectively. Differences between the least square mean changes from Baseline in Schiff sensitivity score and tactile threshold (g) will be presented for the Test Toothpaste compared to Reference Toothpaste (negative control) at Days 28, 14, 7 and 3 from their respective MMRMs, along with two-sided p-values and 95% CIs.

The assumptions of normality and homogeneity of variance in each MMRM will be investigated. In case of violation of these assumptions, a suitable non-parametric test (adjusted for the randomization stratification value) will be performed to assess change from Baseline comparisons (Test Toothpaste vs. Reference Toothpaste at Days 56, 28, 14, 7 and 3, as appropriate); the results will be provided to support the MMRM results.

DHEQ-48

Change from Baseline will be calculated at Day 28 and Day 56 for all DHEQ endpoints.

- **Section 1**
 - Impact on Everyday Life: Q7, Q8 & Q9 (separate scores)
- **Section 2**
 - DHEQ Total Score (sum of Q1-34)
 - DHEQ Restrictions Domain score (sum of Q1-4)
 - DHEQ Adaptation Domain score (sum of Q5-16)
 - DHEQ Social Impact Domain score (sum of Q17-21)
 - DHEQ Emotional Impact Domain score (sum of Q22-29)
 - DHEQ Identity Domain score (sum of Q30-34)
 - DHEQ Global Oral Health (Q35)
 - DHEQ Effect on Life Overall (sum of Q36-Q39)

Change from Baseline will be calculated at the subject-level first then mean change from Baseline will be calculated for each DHEQ endpoint across all subjects.

Change from Baseline for each DHEQ endpoint listed above will be analyzed using a MMRM with time point and maximum Baseline Schiff sensitivity score of the two 'Test Teeth' (2 or 3) as fixed effects, and the respective Baseline DHEQ score as a covariate. Subject will be included

Property of Haleon- Confidential

May not be used, divulged, published or otherwise disclosed without the consent of Haleon

as a repeated measure with unstructured covariance matrix. Kenward-Rogers degrees of freedom will be applied. The estimates of the adjusted mean (SE) change from Baseline will be presented along with 95% Cis for each treatment group.

For each DHEQ endpoint listed above, and each individual DHEQ question, the value at each timepoint (Baseline, Day 28 and Day 56) and the corresponding change from Baseline will be summarized descriptively for each treatment group. Raw means (\pm SE) for each DHEQ endpoint, and the individual DHEQ questions, at each assessment timepoint will be plotted by treatment group.

